14.2 TRIAL STEERING COMMITTEE (TSC)

The TSC will be composed of a majority of independent members. The TSC is an executive committee, reporting to the funder (NIHR) and the sponsor. The TSC is formally appointed by NIHR and members will receive individual letters from NIHR confirming their role. Independent members will be independent of the Sponsor organisations and of any recruiting study sites.

The trial may be prematurely discontinued by the Sponsor, Chief Investigator or Regulatory Authority on the basis of new safety information or for other reasons given by the Data Monitoring Committee / Trial Steering Committee regulatory authority or ethics committee concerned.

If the trial is prematurely discontinued, active participants will be informed, and no further participant data will be collected. The Competent Authority and Research Ethics Committee will be informed within 15 days of the early termination of the trial.

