11.1.4 FOLLOW-UP OF SAES

After the initial SAE report, the Investigator is required to proactively follow each participant and provide further information to the Sponsor on the participant's condition. All SAEs documented at a previous visit/contact and are designated as ongoing, will be reviewed at subsequent visits/contacts. All SAEs will be followed until resolution, until the condition stabilises, until the event is otherwise explained, or until the participant is lost to follow-up. Once resolved, the adverse event log will be updated. The Investigator will ensure that follow-up includes any supplemental investigations as may be indicated to elucidate the nature and/or causality of the SAE. This may include additional laboratory tests or investigations, histopathological examinations, or consultation with other health care professionals. New or updated

information will be recorded on the originally completed SAE form, with all changes signed and dated by the Investigator. The updated SAE form should be resent to the Sponsor.

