11.1.5 Post-study saes

A post-study SAE is defined as any event that occurs outside the SAE detection period. Investigators are not obligated to actively seek SAEs in former study participants. However, if the Investigator learns of any SAE, including death, at any time after a participants has been discharged from the study, and he/she considers the event reasonably related to the investigational product, the Investigator will promptly notify the Sponsor.

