11.1.6 SAEs

SAEs that lead to hospitalisation within 90 days of randomisation will be source data for the primary endpoint and will detail cause of hospitalisation to determine if this was related to COPD or not.

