13.5 INTERIM ANALYSES (STATISTICAL)

No formal interim analysis is planned. An internal pilot phase will assess trial parameters but not the betweenarm effectiveness measures. The DMC will provide advice to the TSC, who will advise the Sponsor in making the final decision on continuing or stopping the trial.

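### The early-termination rule in section 14.2 stops all data collection, which conflicts with SAE follow-up in 11.1.4 and leaves 90-day outcomes incomplete for participants still in the window

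*Protocol*

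**What the plan says.** Section 14.2 of the protocol allows the trial to be stopped early "on the basis of new safety information or for other reasons given by the Data Monitoring Committee" or by other bodies it names. It then gives the rule for that event: "If the trial is prematurely discontinued, active participants will be informed, and no further participant data will be collected". No category of data is exempted.

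Section 11.1.4 sets the duty on SAEs: once an event has been reported, the investigator must keep following that person actively and keep the sponsor informed. The end of that duty is defined by a list, which opens: "All SAEs will be followed until resolution, until the condition stabilises". The only other endpoints given are another explanation for the event and loss to follow-up.

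Section 11.1.5 deals with events after a participant has left the study: "Investigators are not obligated to actively seek SAEs in former study participants". An investigator who nevertheless learns of an SAE and considers it reasonably related must notify the sponsor.

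Section 11.1.6 ties the SAE data to the main result: "SAEs that lead to hospitalisation within 90 days of randomisation will be source data for the primary endpoint". Sections 13.1 and 13.4.1 define the primary outcome as time to first all-cause readmission within 90 days of discharge, taken mainly from HES, with patient report and SAE forms as the fallback.

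Section 13.5 plans no formal interim analysis but keeps a route to stopping open: the DMC advises the TSC, "who will advise the Sponsor in making the final decision on continuing or stopping the trial".

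**The concern.** Two instructions to sites conflict in exactly one situation, an early stop. That situation includes a stop for safety, when the outcome of SAEs still open would be part of the evidence needed to judge the signal.

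The same sentence reaches the primary outcome. Participants discharged fewer than 90 days before the stop would have their follow-up ended there, although their remaining outcome could be obtained by a telephone call or from routine hospital records. The most recent recruits would contribute the shortest follow-up. A statistical analysis plan cannot repair this, because it cannot analyse data that the protocol has told sites not to collect.

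**Working it through.** **Step 1. The rules side by side.** This part needs no arithmetic.

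- 14.2: after a stop, collect nothing further; no exception.
- 11.1.4: continue each SAE until one of four endpoints; a trial stop is not one of them.
- 11.1.5: covers related SAEs that the investigator happens to learn of in people who have left the study. It does not address an SAE already reported and still open, so it does not settle the conflict.
- 4.5.3: a participant who stops the intervention can still be followed for the primary outcome. At participant level, stopping the intervention does not end outcome collection; at trial level, 14.2 says that a stop does.

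**Step 2. Reproduce the design figures (section 13.3).** Inputs: 43% against 34.4% at 90 days, two-sided 5%, 90% power, 1:1 allocation.

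- Hazard ratio = ln(1 − 0.344) / ln(1 − 0.43) = 0.750.
- Events by Freedman's formula = (1.960 + 1.282)² × [(1 + 0.75)/(1 − 0.75)]² = 515, as stated. Schoenfeld's formula gives 508.
- Mean 90-day event probability = (0.43 + 0.344)/2 = 0.387, and 515/0.387 = 1331, as stated. Allowing for 5% withdrawal gives 1398 (1331 × 1.05) to 1402 (1331/0.95), against the stated 1400.

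The design reproduces, so 0.387 is a sound basis for what follows.

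**Step 3. How many participants would be in window.** The protocol states no recruitment period. Assume uniform accrual of 1400 over 18, 24 or 36 months. Number in window = 1400/(months × 30.44) × 90.

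**Step 4. How much of the outcome is still to come.** With uniform accrual, time since discharge among those in window is spread evenly over 0 to 90 days. The expected unobserved first readmissions per person are therefore F(90) minus the mean of F over 0 to 90 days. Two curves through the protocol's 23% at day 30 and 43% at day 90:

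- Weibull, shape 0.70, hazard ratio 0.75, arms averaged: 0.387 − 0.244 = 0.143.
- Straight lines between 0, 23% and 43%, with a 20% relative reduction in one arm (so × 0.9 on average): the control mean is (0.115 × 30 + 0.33 × 60)/90 = 0.2583, giving 0.9 × (0.43 − 0.2583) = 0.1545.

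**Step 5. Events left unobserved.** A stop at half enrolment means 700 randomised, who would yield 700 × 0.387 = 271 events with complete follow-up. A 5% loss applied to both numerator and denominator leaves the share unchanged.

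| Accrual (months) | In window | Unobserved, Weibull | Unobserved, linear | Share of 271 |
|---|---|---|---|---|
| 18 | 230 | 33 | 35.5 | 12–13% |
| 24 | 172 | 25 | 26.6 | 9–10% |
| 36 | 115 | 16 | 17.8 | 6–7% |

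**The case against.** The best defence is that 11.1.4 is the general rule for a running trial and 14.2 the special rule for its termination, with participant data meaning scheduled trial data and not safety reporting to the sponsor. That reading is possible, but the text does not state it, and sites would have to guess. The conflict stands as one of wording to be reconciled.

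Other parts of the defence succeed and limit the point:

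- A reader might infer that the rule discards the 90-day outcomes of everyone already randomised. It does not. Nothing collected is deleted, and anyone past day 90 with data in hand keeps a full outcome.
- A reader might infer that the treatment comparison would be biased. Censoring at a calendar date common to both arms loses information but does not by itself bias a log-rank, Kaplan-Meier or Cox analysis.
- A reader might infer that HES linkage is forbidden after a stop. Section 14.2 does not mention linkage, which section 13.7 describes as done by a third party through the NHS number. Whether a later extract counts as further collection is open.
- A reader might set the lost events against 515. A trial stopped during recruitment would not reach 515 events, so that denominator is wrong.
- The rule never operates if the trial runs to plan, and no formal interim analysis is planned.

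It can also be argued that censoring at the stop is the cleaner choice, because delivery of the intervention may change afterwards. That is a reason for a sensitivity analysis. It is not a reason to leave the data uncollected.

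**Conclusion.** The point holds as a conflict between 14.2 and 11.1.4 that 11.1.5 does not resolve, and as a rule that, read literally, leaves the rest of the 90-day follow-up uncollected for participants in window at an early stop. The conflict rests on the text alone.

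The size is illustrative. It assumes uniform accrual over 18 to 36 months, a readmission curve fitted to the protocol's two rates, and a stop at half enrolment: about 115 to 230 participants in window and about 16 to 35 first readmissions unobserved, roughly 6 to 13% of the events then expected. The share would be larger for an earlier stop and smaller for a later one. The loss is one of information and of safety outcomes, contingent on early termination. The documents do not support a claim that existing data are lost or that the comparison would be biased.

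**What to change.** Reconcile 14.2 with 11.1.4. Section 14.2 could state that on premature discontinuation no further participants are randomised; SAEs open at that date continue to be followed under 11.1.4; and primary-outcome and SAE data for participants already randomised are completed to day 90, including HES linkage, unless the REC or sponsor directs otherwise. Add a sensitivity analysis of the primary outcome with censoring at the termination date, in case delivery of the intervention changes after the stop.

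The cost is a short protocol amendment and, only if the trial does stop early, follow-up calls and linkage for up to 90 days afterwards. The change concerns data collection alone; whether treatment continues after a stop is a separate matter and is not addressed here.

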14.3 DATA MONITORING COMMITTEE (DMC)

The DMC will be composed of three independent members: a statistician and two clinicians. The DMC is an advisory committee, reporting to the Trial Steering Committee. The DMC is formally appointed by NIHR and

members will receive individual letters from NIHR confirming their role. Members will be independent of the Sponsor organisations and of any recruiting study sites. The DMC will work to the DAMOCLES guidance⁽³⁹⁾.

14.4 MONITORING

The Investigator(s) will permit trial-related monitoring, audits, REC review, and regulatory inspections by providing the Sponsor(s), Regulators and REC direct access to source data and other documents (e.g., participants' case sheets, blood test reports etc.). The routine site monitoring activities will be performed remotely by the Trial Manager.

15. MISCELLANEOUS

15.1 PLANS FOR INDEPENDENT AUDIT

There are no current plans to commission an independent audit of study conduct.

15.2 **DISSEMINATION PLANS**

The primary and secondary outcomes will be published in a peer reviewed open-source medical journal within 12 months of the end of trial. Recruiting sites will be informed of the results and will be asked to disseminate the findings to participants. Patient groups will be informed of the results for dissemination among their members.

15.3 END OF TRIAL

The end of the trial will be defined as database lock.

15.4 CONFIDENTIALITY

When consent forms are signed, a copy will be provided to the participant, a copy will be filed in the medical records and the original will be retained in the Investigator Site File. Participant's year of birth and age will be entered into the study database from countries where this is permitted, but no more identifying information will be collected outside the recruiting study site. Within site, an Investigator Site File will be maintained by the site PI. Participants will be fully identifiable within these files.

When the study is complete, a data sharing dataset will be created from the raw data by the study analyst, which will not include any other identifiable data and study PIN will be altered so that individuals are not recognisable from the dataset.

The study will comply with the General Data Protection Regulations (GDPR).

15.5 FUNDING

This study has been funded by the NIHR HTA (application NIHR156698).

15.6 INSURANCE AND INDEMNITY

This study is co-sponsored by King's College London (KCL) and Guys and St Thomas' NHS Foundation Trust (GSTFT). The co-sponsors will, at all times, maintain adequate insurance for the design, management and conduct of the study: (a) KCL through its' own professional indemnity (Clinical Trials) & no fault compensation policy; and (b) GSTFT through NHS Resolution cover, in respect of any claims arising as a result of negligence by its employees, brought by or on behalf of a study participant.

15.7 **ARCHIVING**

Upon request, KCTU will provide a copy of the final exported dataset to the CI in .csv format and the CI will distribute as appropriate for the purpose of archiving. The CIs will appoint named individuals within the

research team to be responsible for archiving the documents which are, or have been, contained in the trial master file and, access to those documents shall be restricted to those appointed individuals. At the end of the trial, all trial data will be stored and archived in line with Sponsor requirements.

15.8 DATA CONTROLLER

Guy's and St Thomas' NHS Foundation Trust (GSTFT) and King's College London (KCL) as co-sponsors of the research study have shared Data Controller responsibilities and agree to comply with the Data Protection Legislation including UK GDPR. The data generated in the process of the study will flow into KCL and no data flow outside of KCL will occur.

Where optional samples have been collected (samples containing no human tissue, cells or DNA), they may be stored and used for further research purposes according to the appropriate research protocols and with relevant material/data transfer agreements in place.

15.9 INTELLECTUAL PROPERTY (IP)

There will be no IP generated as a result of the study.

